5.3.2.4. Endpoints for Correlation

Correlations will be evaluated graphically with scatter plots and heat maps displaying such potential associations by intervention arm and/or selected subgroups (baseline NA treatment duration, age, and baseline HBsAg).

The following correlation coefficients will be calculated by study intervention arm for the different correlation scenarios:

- Pearson's correlation coefficient for two continuous variables.
- Phi correlation coefficient for two binary variables.
- Point biserial correlation coefficient for one binary variable and one continuous variable.

5.4. Exploratory Endpoints

5.4.1. Definitions

5.4.1.1. Binary Endpoints

5.4.1.1.1. Partial Cure

Partial cure will be evaluated at each of the following time points separately: 24 weeks and 48 weeks after stopping all study interventions. A participant will be defined as having achieved partial cure if he/she has:

- Stopped all study interventions at any time, and
- had HBV DNA level $< 2,000$ IU/ml quantifiable at the given week of interest, and
- had HBsAg \geq LLOQ at the given week of interest, and
- not required NA re-treatment after stopping all study interventions.

If the HBV DNA or HBsAg value 24 weeks after stopping all study interventions is missing, the LOCF in conjunction with the next available observation imputation approach will be used. The available non-missing lab test closest to 24 weeks after stopping all study interventions which is no earlier/later than 12 weeks from the actual time point of interest (12 and 36 weeks after stopping all study interventions, respectively) will be imputed. If a subject does not have data within 12 and 36 weeks after stopping all study interventions then the subject will be considered as a non-responder.

If the HBV DNA or HBsAg value at 48 weeks after stopping all study interventions is missing, the LOCF imputation approach will be used. The last available lab test no earlier than 36 weeks after stopping all study interventions will be carried forward. If a subject does not have data 36 weeks after stopping all study interventions then the subject will be considered as a non-responder.

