5.1.2. Data Handling Rules

Those measurements collected from screening visit to the end of study will be handled according to the following rules in [Table 3](#).

Table 3: Data Handling Rules for HBV Virology and Serology Assessments

HBV parameter	LLOQ	ULOQ	Imputed Values	
			If value < LLOQ	If value > ULOQ
HBsAg	0.05 IU/mL	124,925.00 IU/mL w/o dilution	0.025 IU/mL ^(a)	137,417.50 IU/mL w/o dilution ^(b)
		249,750.00 IU/mL with dilution		274,725.00 IU/mL ^(b) with dilution
HBeAg	0.11 IU/mL	1,400.00 IU/mL w/o dilution	0.055 IU/mL ^(a)	1,540.00 IU/mL ^(b) w/o dilution
		7,000.00 IU/mL with dilution		7,700.00 IU/mL ^(b) with dilution
HBcrAg*	$3.0 \log_{10}$ U/mL	7.0 \log_{10} U/mL w/o dilution	2.7 \log_{10} U/mL	$7.7 \log_{10}$ U/mL ^{(b)(c)} w/o dilution
		9.0 \log_{10} U/mL with dilution		$9.9 \log_{10}$ U/mL ^(b) with dilution
HBV DNA	20 IU/mL	170,000,000 IU/mL w/o dilution	If target detected: 15 IU/mL If target not detected: 5 IU/mL	187,000,000 ^{(b)(c)} w/o dilution

Table 3: Data Handling Rules for HBV Virology and Serology Assessments

HBV parameter	LLOQ	ULOQ	Imputed Values	
			If value < LLOQ	If value > ULOQ
HBV RNA*	LLOQ = 4.04 \log_{10} cp/mL LOD = 2.49 \log_{10} cp/mL	NAP	If <LOD or target not detected then 2.19 \log_{10} cp/mL	NAP
Anti-HBs	5mIU/mL	10000.0 mIU/mL	2.5 mIU/mL ^(a)	11000.0 mIU/mL ^(b)

* As new assays become available different data handling rules may apply

Key: NAP=Not applicable

(a) LLOQ/2

(b) ULOQ+(ULOQ/10)

(c) If the original result > ULOQ, then take the re-test value (i.e. diluted result). If the diluted result is not available, use the imputed value indicated in this table

All other viral activity data with values <LLOQ which are not included in the data handling rules above will be imputed by the absolute value divided by 2.

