5.3.1.1.2. Suppressed HBV DNA

HBV DNA < LLOQ and HBV DNA TND will be evaluated over time.

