5.3.1.1.3. Thresholds Based on HBsAg and HBV DNA

The following blood marker reduction/seroclearance thresholds over time on treatment, and at 12, 24, 36 and 48 weeks, respectively, after stopping all study interventions (including NA) and not having NA re-treated will be evaluated.

- **HBsAg <LLOQ and HBV DNA**
 - HBsAg <LLOQ and HBV DNA <LLOQ**
 - HBsAg <LLOQ and HBV DNA \geq LLOQ
- **HBsAg \geq LLOQ and HBV DNA <2,000 IU/ml**
 - HBsAg \geq LLOQ and HBV DNA <LLOQ**
 - HBsAg \geq LLOQ and LLOQ \leq HBV DNA <2,000 IU/ml (See partial cure in Section 5.4.1.1.1)
- **HBsAg \geq LLOQ and HBV DNA \geq 2,000 IU/ml**
 - HBsAg <100 IU/mL and HBV DNA \geq 2,000 IU/ml
 - HBsAg \geq 100 IU/mL and HBV DNA \geq 2,000 IU/ml

** HBV DNA<LLOQ will be summarized by DNA TD, TND and overall.

Due to the exploratory objectives of this Phase 2b study, additional blood marker reduction/seroclearance thresholds may also be added at a later point in time according to the clinical interest.

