5.3.1.4. Endpoints for Correlation

Correlations between baseline characteristics, and on-treatment HBV blood markers and/or their change from baseline at Week 24 and 48 with off-treatment endpoints will be evaluated. The list of HBV blood markers, including but not limited to, are defined below:

Off treatment HBV marker	Baseline Characteristics/On treatment HBV marker
HBsAg change from baseline at FU Week 12	
 • Age • Baseline NA treatment duration • HBsAg value at baseline • HBsAg change from baseline at Week 24 • HBsAg change from baseline at Week 48
HBsAg change from baseline at FU Week 24	
 • Age • Baseline NA treatment duration • HBsAg value at baseline • HBsAg change from baseline at Week 24 • HBsAg change from baseline at Week 48
HBsAg change from baseline at FU Week 48	
 • Age

Off treatment HBV marker	Baseline Characteristics/On treatment HBV marker
	
 • Baseline NA treatment duration • HBsAg value at baseline • HBsAg change from baseline at Week 24 • HBsAg change from baseline at Week 48
HBsAg seroclearance at FU week 24 (Yes;No)	
 • Age • Baseline NA treatment duration • HBsAg value at baseline • HBsAg change from baseline at Week 48 • HBsAg value at Week 48 • HBsAg seroclearance at week 24 (Yes;No) • HBsAg seroclearance at week 48 (Yes;No) • Anti-HBe antibodies status at week 48 (Positive:Negative)
HBsAg seroclearance at FU week 48 (Yes;No)	
 • Age • Baseline NA treatment duration • HBsAg value at baseline • HBsAg change from baseline at Week 48 • HBsAg value at Week 48 • HBsAg seroclearance at week 24 (Yes;No) • HBsAg seroclearance at week 48 (Yes;No) • Anti-HBe antibodies status at week 48 (Positive:Negative)
Partial cure (Yes;No) at FU Week 24 (Yes;No)	
 • Age • Baseline NA treatment duration • HBsAg value at baseline • HBsAg value at Week 48 • HBsAg seroclearance at week 24 (Yes;No) • HBsAg seroclearance at week 48 (Yes;No) • Anti-HBe antibodies status at week 48 (Positive:Negative)
Partial cure (Yes;No) at FU Week 48 (Yes;No)	
 • Age • Baseline NA treatment duration • HBsAg value at baseline • HBsAg value at Week 48 • HBsAg seroclearance at week 24 (Yes;No) • HBsAg seroclearance at week 48 (Yes;No) • Anti-HBe antibodies status at week 48 (Positive:Negative)

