5.3.2.1. Binary Endpoints

The number and proportion (%) of participants achieving the endpoints defined in Section 5.3.1.1 will be summarized. The associated 90% CI may also be included.

The following binary endpoints will be compared between treatment arms using a 2-sided 90% CI of the difference in proportions between the treatment groups (Arm 1 minus Arm 2) that will be constructed using a Mantel-Haenszel test controlling for stratification factors, i.e., HBsAg level (<1,000 IU/mL or \geq 1,000 IU/mL), race (Asian versus non-Asian) and type of NA (TDF/TAF versus ETV):

- HBsAg seroclearance:
 - at Week 48
 - at Week 96 (ie, 48 weeks after completion of all study interventions at Week 48) without restarting NA treatment,
 - 24 weeks after stopping all study interventions (regardless when intervention was stopped) without restarting NA treatment, and
 - 48 weeks after stopping all study interventions (regardless when intervention was stopped) without restarting NA treatment

Bar charts will be provided for selected endpoints for proportions (%) in each intervention arm.

Cumulative percentage of participants achieving any given decrease from baseline at Week 72 and Week 96 in HBsAg and HBV DNA (Section 5.3.1.1.5) will be presented graphically.

Subsections below describe the additional analyses planned for only those specific other secondary binary endpoints that require further evaluations.

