5.3.2.2.1. HBsAg and HBV DNA

The change from baseline value to the nadirs (i.e. maximum decrease for each participant) in HBsAg and HBV DNA will be summarized descriptively by intervention arm. Box plots of the changes to nadirs in HBsAg and HBV DNA will display the distribution by intervention arm.

Change from baseline based on \log_{10} transform for quantitative HBsAg and HBV DNA will be analyzed using mixed effects model for repeated measures [MMRM]) including intervention arm, analysis time point (week), their interaction, and 3 randomization stratification factors (screening HBsAg level [$<1,000$ IU/mL or $\geq 1,000$ IU/mL], race [Asian versus non-Asian] and type of NA [TDF/TAF versus ETV]) and baseline blood marker categorical variable as fixed effects. In addition, the above model will be augmented with an intervention arm-by-analysis week interaction term (i.e. treatment-by-time interaction term) to evaluate the change of treatment effect over time and the intervention arm-by-baseline interaction term. The covariance structure will include a random intercept at the level of the participant to capture between-participant variability, while within-participant variability will be captured with an unstructured (type=UN) covariance matrix. In case of convergence problems, simpler variance-covariance structures such as Toeplitz or AR (1) will be considered. The selection of any of these structures will be determined after exploration of the observed correlation structure. The LS mean of change from baseline, standard error (SE), 90% confidence interval (CI) and p-values will be provided.

Descriptive statistics on actual values (original unit and \log_{10} transformed values) and changes from baseline (\log_{10} transformed values) at end of treatment in HBsAg and HBV DNA will be summarized by study intervention arm by outcome response (i.e. by functional cure status at Week 72, and by partial cure status at Week 72).

Spaghetti plots for both absolute values and changes from baseline of HBsAg and HBV DNA will be presented over time per blood marker by intervention arm and by selected subgroups (e.g. HBV Genotype) and by outcome response (i.e. by functional cure status at Week 72, and by partial cure status at Week 72).

Cross-tabulations overtime and overall of quantitative versus qualitative HBsAg values will also be presented.

Shift tables in HBV DNA categories from baseline will also be summarized by study intervention arm.

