5.4.2.1. Binary Endpoints

The number and proportion (%) of participants achieving the endpoints defined in Section 5.4.1.1 will be summarized. The associated 90% CI may also be included.

Participants who achieve partial cure at 24 weeks and 48 weeks after stopping all study interventions will be compared between treatment interventions using the Mantel-Haenszel test and 90% CIs adjusted for the stratification factors. Similar analysis for the impact of finite treatment duration on functional cure will also be done.

Shift tables in Anti-HBe positive/negative values from baseline will also be provided at each time point.

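### The SAP's exploratory partial cure endpoint counts off-treatment, HBsAg-positive participants with HBV DNA below LLOQ as not achieving it

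*SAP*

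**What the plan says.** SAP 5.4.1.1.1 defines partial cure, at 24 and 48 weeks after stopping all interventions, by four conditions: all study interventions stopped, HBV DNA below 2,000 "IU/ml quantifiable at the given week of interest", HBsAg at or above LLOQ, and no NA re-treatment since stopping.

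SAP 5.3.1.1.3 makes clear how the third word of that phrase operates. Under the parent category of HBsAg at or above LLOQ with HBV DNA below 2,000 IU/mL it lists two rows. One is HBV DNA below LLOQ. The other runs from LLOQ upward and carries the cross-reference: "HBV DNA <2,000 IU/ml (See partial cure in Section 5.4.1.1.1". Only the second row is labelled partial cure.

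The variable is then used in three places:

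- **Arm comparison (SAP 5.4.2.1).** Partial cure at 24 and 48 weeks "will be compared between treatment interventions using the Mantel-Haenszel test and 90% CIs adjusted for the stratification factors".
- **Correlations (SAP 5.3.1.4).** The off-treatment outcomes include "Partial cure (Yes;No) at FU Week 24 (Yes;No", and the same at follow-up Week 48.
- **Grouped displays (SAP 5.3.2.2.1).** HBsAg and HBV DNA are presented "by functional cure status at Week 72, and by partial cure status at Week 72".

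Protocol 9.4.1.2 plans a Mantel-Haenszel (MH) comparison of a related endpoint called partial response, described only as HBV suppression with no return to NA. It states no lower limit on HBV DNA.

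**The concern.** An endpoint named as a degree of cure should not turn from yes to no because viral suppression becomes deeper while everything else stays the same. Here it does. Someone at 1,500 IU/mL achieves it, while someone with HBV DNA not detected is grouped with those at 2,000 IU/mL or above and those who needed re-treatment.

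Other parts of the SAP point the opposite way. Section 5.3.1.1.2, under a heading about suppressed HBV DNA, says that "HBV DNA < LLOQ and HBV DNA TND will be evaluated over time". The partial response endpoint in the protocol, read naturally, would also include these participants.

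Two consequences follow. In the arm comparison, an arm with more participants below LLOQ loses ground for that reason alone. In the correlations and grouped displays, the group without partial cure mixes deep suppression with rebound, which can blur or distort associations even if the arms do not differ.

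**Working it through.** **Step 1. Apply the rule.** The plan gives no figure for partial cure to reproduce, so the check starts from the classification. SAP Table 3 (5.1.2) sets the HBV DNA LLOQ at 20 IU/mL and assigns values below it as follows: "If target detected: 15 IU/mL If target not detected: 5 IU/mL". Both values are under 2,000, so only the lower bound excludes them. For a participant who is HBsAg-positive, off treatment and not re-treated:

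| HBV DNA (IU/mL) | SAP partial cure | Parent category (<2,000, including <LLOQ) |
|---|---|---|
| 5 (target not detected) | No | Yes |
| 15 (target detected) | No | Yes |
| 20 | Yes | Yes |
| 1,500 | Yes | Yes |
| 2,500 | No | No |

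**Step 2. Effect on the arm difference.** Let q be the proportion in an arm with HBsAg at or above LLOQ, HBV DNA below LLOQ, off treatment and not re-treated. In each arm, SAP partial cure = parent category − q. Hence

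SAP difference = parent difference − (q1 − q2).

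The MH-weighted difference is linear in the stratum proportions, so the identity holds there too. Over 8 strata in 2,000 simulated datasets the largest error was 1.1e-16. The shift is zero when q1 = q2 and cannot exceed the larger of the two. If q is at most 5% in each arm, the shift is at most 5 points.

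**Step 3. Illustration.** The documents give no off-treatment rates, so these counts are assumptions. N = 80 and 40, unadjusted Wald 90% CI: d ± 1.645 × √[p1(1−p1)/80 + p2(1−p2)/40].

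| Parent category | Excluded (<LLOQ) | SAP partial cure | Difference in points (90% CI) |
|---|---|---|---|
| 40/80 v 12/40 | not applied | not applied | +20.0 (+4.9 to +35.1) |
| 40/80 v 12/40 | 8 v 4 | 32/80 v 8/40 | +20.0 (+6.2 to +33.8) |
| 40/80 v 12/40 | 8 v 2 | 32/80 v 10/40 | +15.0 (+0.6 to +29.4) |
| 40/80 v 12/40 | 16 v 4 | 24/80 v 8/40 | +10.0 (−3.4 to +23.4) |
| 32/80 v 12/40 | not applied | not applied | +10.0 (−4.9 to +24.9) |
| 32/80 v 12/40 | 8 v 4 | 24/80 v 8/40 | +10.0 (−3.4 to +23.4) |
| 32/80 v 12/40 | 8 v 2 | 24/80 v 10/40 | +5.0 (−9.1 to +19.1) |
| 32/80 v 12/40 | 16 v 4 | 16/80 v 8/40 | 0.0 (−12.7 to +12.7) |

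Worked example, fourth row: 16/80 = 20% and 4/40 = 10%, so the shift is 10 points and 20.0 − 10.0 = 10.0.

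**Step 4. What the parent category still leaves out.** It keeps HBsAg at or above LLOQ, so functional cures remain No. Take the planning rates (5% control plus 20 points): 20/80 v 2/40 functional cures. Assume that all of them have HBV DNA below 2,000 IU/mL without re-treatment, and that this state totals 40/80 v 12/40 whatever the HBsAg. Partial cure on the parent category is then (40 − 20)/80 v (12 − 2)/40 = 20/80 v 10/40, or 25% v 25%, a difference of 0. Functional-or-partial cure is 40/80 v 12/40, a difference of +20.0.

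**Step 5. Flare dating (minor).** In SAP 5.3.1.1.6 the virologic flare start date and peak category need two consecutive visits or values, and so does the biochemical flare start date. The footnote also accepts the last observed time point alone as confirmation, and 5.3.1.1.7 does the same for breakthrough. Sections 5.3.1.3.2 and 5.3.1.3.3 date the event at the first of two confirmation visits. With the 200 IU/mL limit, the series 5, 5, 300, 400, 5 is a flare dated at the third visit. The series 5, 5, 5, 5, 5,000 is a flare with no date.

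**The case against.** The strongest defence is that 5.3.1.1.3 sets out mutually exclusive rows and partial cure is simply the name of one. The SAP does not state that intent, but the table reads that way. This explains the table. It does not make a middle row a sound endpoint for a comparison of success rates.

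A second defence is that nothing is lost. The parent category and the below-LLOQ row are both tabulated at 12, 24, 36 and 48 weeks after stopping, and 5.3.2.1 allows a 90% CI on each proportion. Protocol 9.4.1.2 also plans MH comparisons of HBV DNA below LLOQ at Weeks 72 and 96. This stands: a reader might infer that these participants vanish from reporting, and they do not. The remaining gap is narrower. In SAP 5.3.2.1 the list introduced by "The following binary endpoints will be compared between treatment arms using a 2-sided 90% CI of the difference in proportions" contains only HBsAg seroclearance, and 5.4.2.1 does not add the parent category.

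Third, calling HBV DNA below LLOQ the better state is partly inference. Protocol 2.1 discusses viral relapse after stopping NA as a possible trigger for later HBsAg loss. That is a fair reason to display the two HBV DNA rows separately, but not to score the suppressed row as a failure.

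Fourth, widening the category does not make the endpoint monotone, as step 4 shows. This stands and shapes the fix.

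Finally, a reader might say that the SAP contradicts the protocol. That is too strong: the protocol's partial response has no HBsAg condition and no HBV DNA threshold, so the SAP definition fits it poorly rather than breaking a stated rule.

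**Conclusion.** The point holds. As written, partial cure excludes the most suppressed HBsAg-positive participants and places them with those who rebounded or were re-treated, in one planned comparison, the correlations and the grouped displays. The change is worth making because the SAP already contains the better category.

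The consequence is limited. The endpoint is exploratory, the comparisons carry no multiplicity adjustment, and the primary endpoint and its analysis are untouched. A reader might infer a bias against the investigational arm. The documents do not support that: the shift equals q1 − q2, they give no value for either, and it is zero if the arms match. Protocol 2.1 expects HBV DNA rebound in most patients after stopping NA, so both proportions may be small. The intervals in step 3 rest on assumed counts and ignore stratification.

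The flare and breakthrough issue is a clarification only. It can make incidence and time-to-event outputs disagree for the same participant, and its frequency cannot be derived from the documents.

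**What to change.** 1. Define partial cure as the parent category in SAP 5.3.1.1.3: HBsAg at or above LLOQ and HBV DNA below 2,000 IU/mL, including below LLOQ whether or not target is detected, with all interventions stopped and no NA re-treatment. Use it for the MH comparison, the correlations and the grouped displays. Keep the below-LLOQ row and the row from LLOQ up to 2,000 as descriptive sub-categories.
2. Present the comparison next to functional cure, or add a comparison of functional-or-partial cure. State that partial cure alone is not a measure of benefit, since functional cures count as No.
3. State one dating rule for events confirmed only at the last observed time point, for example the date of that value. Apply it alike to virologic flares, biochemical flares and virologic breakthrough, and align the wording on peak category.

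Cost: SAP wording and derivation code only, with no new data. Partial cure counts and some event dates will change. Peak categories may also change, depending on how the confirmation wording is aligned.

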5.4.1.1.2. HBV RNA and HBcrAg

The cut-offs for HBV RNA level are as follows:

- < TND
- < LOD
- < LLOQ
- < 1000 copies/mL

The cut-offs for HBV RNA change from baseline are as follows:

- decrease by $\geq 1 \log_{10}$ copies/mL
- decrease by $\geq 2 \log_{10}$ copies/mL
- decrease by $\geq 3 \log_{10}$ copies/mL

The cut-offs for HBcrAg level are as follows:

- <3.0 log U/mL
- <4.0 log U/mL

The cut-offs for HBcrAg change from baseline are as follows:

- decrease by $\geq 1 \log$ U/mL
- decrease by $\geq 2 \log$ U/mL
- decrease by $\geq 3 \log$ U/mL
- decrease by $\geq 4 \log$ U/mL

5.4.1.1.3. Anti-HBe Antibodies

Participants who have positive and negative Anti-HBe values will be evaluated over time.

5.4.1.1.4. Impact of Finite Treatment Duration on Functional Cure

The following exploratory analysis will be performed to have a better understanding of the impact of finite treatment duration and of the below criteria to stop NA treatment after 48 weeks of treatment on the outcome of HBsAg seroclearance 24 weeks off treatment.(functional cure).

For this finite treatment duration analysis, a participant will be defined as having functional cure at Week 72 (responder) if he/she has:

- completed 48 weeks of treatment, and
- met the following criteria at Week 44:
 - The participant has ALT <3x ULN, AND
 - The participant has HBV DNA <LLOQ, AND
 - The participant is HBeAg-negative, AND
 - The participant has HBsAg <10 IU/mL.
- had HBsAg seroclearance at Week 72 (i.e. 24 weeks after end of study intervention), and

- not required NA re-treatment between Weeks 48 and 72.

Participants who withdraw from the study prior to Week 72 will be considered as non-responders. All participants with missing data for the determination of the status will be imputed as non-responders.

5.4.1.1.5. Treatment Failure

Treatment failure and the reasons will be evaluated based on observed case data. A participant will be defined as a treatment failure at Week 72 if he/she never achieves functional cure (see Section 5.2.1) at Week 72.

The reasons for not achieving functional cure are as follows:

- HBsAg \geq LLOQ at Week 72
- required NA re-treatment between Week 48 and 72

Similarly, a participant will be defined as having treatment failure at Week 96 for either of the following reasons:

- HBsAg \geq LLOQ at Week 96
- required NA re-treatment between Week 48 and 96

5.4.1.2. Continuous Endpoints

Severity of liver disease at the end of study intervention and follow-up versus baseline will be evaluated by the changes in fibrosis according to Fibroscan liver stiffness measurements.

Actual values and changes from baseline (log transformed value) over time in HBV RNA, HBV HBcrAg and anti-HBs will be evaluated.

Change will be defined as: value at a given time point minus baseline value.

The change from baseline value to the nadir (i.e. maximum decrease for each participant) in HBV RNA and HBcrAg will be evaluated at three intervals: on-treatment nadir, during follow-up nadir, and entire study duration nadir.

